## 7.2. Objective 2: Treatment Patterns

### 7.2.1. Treatment Patterns (sequence)

**Table 3. Summary of Treatment Patterns by Line of Treatment and Regimen within Line**

Progression-Based Line Agent	Overall (n=xx)	
	Patients N=xxx	%
L1R1: [agent, agent, agent]..., L1R2: [agent, agent, agent]...L2R1: [agent]...	n	(x.x%)
L1: [agent, agent, agent]...	n	(x.x%)
L1: [agent, agent, agent]...	n	(x.x%)
L1: [agent, agent, agent]...	n	(x.x%)

L denotes progression-based line; A denotes agent.

Regimens within each line for the first three lines of therapy after the index date.

### 7.2.2. Treatment Characteristics, Overall and by First Line Therapy Type

**Table 4. Treatment Characteristics**

	N=xxx
Dose Change	
First Line Therapy	
Starting Dose	
n	xx
Mean	x.x
SD	x.x
1 st Quartile	x.x
Median	x.x
3 rd Quartile	x.x
IQR	x.x
Min, Max	x.x,x.x
Dose Titration (Dose Increase Immediately Following Initiation*), n (%)	n (x.x%)
Dose Increase (Not Immediately Following Initiation), n (%)	n (x.x%)
Dose Titration (Dose Decrease Immediately Following Initiation*), n (%)	n (x.x%)
Dose Decrease (Not Immediately Following Initiation), n (%)	n (x.x%)

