## 8. RESEARCH QUESTION AND OBJECTIVES

The study includes patients with a diagnosis of AML who received Mylotarg in a real-world setting.

The study objectives are as follows. All analyses as described in Objectives 1 through 4 will be assessed across all patients using Mylotarg, and will not be stratified by a grouping variable.

1. To describe the demographic and clinical characteristics as outlined in the variable list below for patients diagnosed with AML who received Mylotarg in a real-world setting.
  - a. Demographic characteristics will include age, race, body mass index (BMI), insurance status, and region of residence closest to the date of AML diagnosis.
  - b. Clinical characteristics will include comorbidity scores, Eastern Cooperative Oncology Group (ECOG) score, and disease characteristics such as stage at index date, cytogenetic testing results at index date, and de novo versus secondary AML diagnosis.
2. To describe the treatment patterns from the diagnosis of AML through the end of the third relapsed/refractory (R/R)-based line of therapy (R/R event, or disease progression, or death are considered as end events).
  - a. Distribution of regimens within lines, for the first 3 R/R-based lines of systemic therapy.
  - b. Distribution of regimen sequences, across 3 R/R-based lines of systemic therapy.
  - c. Starting dose and dose changes of Mylotarg in each of the 3/R/R-based lines of therapy.
  - d. Duration of Mylotarg treatment in each of the first three R/R-based line of therapy.
3. To describe the effectiveness outcomes of treatment of AML patients who received Mylotarg in a real-world setting.
  - a. Real world event-free survival (rwEFS)/real world relapse-free survival (rwRFS) in the first three R/R-based lines of therapy. The definition of rwEFS/rwRFS as described in [Section 9.7.2](#) is aligned to the extent possible using real world data with that used by Pfizer in other studies.
  - b. Real world overall survival (rwOS) from start of the initial line of therapy in which Mylotarg is used.

- c. rwEFS/rwRFS/rwOS will be described across all patients.
4. To evaluate tumor response for the first qualifying Mylotarg-containing R/R-based line of therapy among AML patients who received Mylotarg in a real-world setting.
  - a. First and best tumor response, as described in [Section 9.7.6](#), will be described in the first qualifying Mylotarg-containing R/R-based line of therapy.

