## 2. OBJECTIVES

The study includes patients with a diagnosis of AML who received Mylotarg (Gemtuzumab ozogamicin) in a real-world setting.

The study objectives are as follows. All analyses as described in Objectives 1 through 4 will be assessed across all patients using Mylotarg and will not be stratified by a grouping variable.

1. To describe the demographic and clinical characteristics as outlined in the variable list below for patients diagnosed with AML who received Mylotarg in a real-world setting.
  - a. Demographic characteristics will include age, race, body mass index (BMI), insurance status, and region of residence closest to the date of AML diagnosis.
  - b. Clinical characteristics will include comorbidity scores, Eastern Cooperative Oncology Group (ECOG) score, and disease characteristics such as stage at index date, cytogenetic testing results at index date, and de novo versus secondary AML diagnosis.
2. To describe the treatment patterns from the diagnosis of AML through the end of the third relapsed/refractory (R/R)-based line of therapy (R/R event, or disease progression, or death are considered as end events).

- a. Distribution of regimens within lines, for the first 3 R/R-based lines of systemic therapy.
  - b. Distribution of regimen sequences, across the first 3 R/R-based lines of systemic therapy.
  - c. Starting dose and dose changes of Mylotarg in each of the first 3 R/R-based lines of therapy.
  - d. Duration of Mylotarg treatment in each of the first 3 R/R-based line of therapy.
3. To describe the effectiveness outcomes of treatment of AML patients who received Mylotarg in a real-world setting.
    - a. Real-world event-free survival (rwEFS)/real-world relapse-free survival (rwRFS) in the first 3 R/R-based lines of therapy. The definition of rwEFS/rwRFS as described in [Section 4.3.2](#) is aligned to the extent possible using real-world data with that used by Pfizer in other studies.
    - b. Real-world overall survival (rwOS) from start of the initial line of therapy in which Mylotarg is used.
    - c. rwEFS/rwRFS/rwOS will be described across all patients.
  4. To evaluate response for each regimen in the first qualifying Mylotarg-containing R/R-based line of therapy among AML patients who received Mylotarg in a real-world setting.
    - a. First and best response, as outlined in [Section 4.3.6](#) will be described for each regimen in the first qualifying Mylotarg-containing R/R-based line of therapy.

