### 3.4. Eligibility Criteria

#### 3.4.1. Inclusion Criteria

Patients must meet all of the following inclusion criteria to be eligible for inclusion in the study:

1. Confirmed diagnosis of AML on or after 01 December 2014 through Clinical Research Nurse (CRN) review of provider documentation of AML diagnosis in the medical record.
2. Receipt of Mylotarg at any point during first 3 R/R-based lines of therapy following initial AML diagnosis date occurring on or after 9/1/2017.
3. Age  $\geq 18$  years at initial diagnosis of AML.

There are no inclusion criteria related to minimum follow-up.

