### 3.5.2. Derived Variables

Variables derived from abstracted and extracted data will include the following:

- Age at index date (Table 1).
- BMI at index date ( $\pm 30$  days) (Table 1).
- Geographic census region of patient's residence (Table 1).
- Weighted index of comorbid disease condition. Weighting of comorbid conditions will follow the weighting as specified in the Charlson Comorbidity Index (Table 2).
- Start and end dates and start and end dose of infused anti-cancer treatments from the index date through the end of the third R/R-based line of therapy or the end of the record, whichever occurs first.
- Dose changes of all oral (if applicable), infused, or injected anti-cancer therapies from the index date through the end of the first R/R-based line of therapy or the end of the record, whichever occurs first (Table 4).
- Start and end schedule of infused anti-cancer treatments from the index date through the end of the third R/R-based line of therapy or the end of the record, whichever occurs first (Table 3-Table 5).
- Treatment regimens, derived from oral and infused agents delivered, including start and stop dates, and indication of subsequent treatment after 1L (Table 3-Table 5).
- Duration of anti-cancer treatments regimens from the index date through the end of the third R/R-based line of therapy or the end of the record, whichever occurs first. Duration will be calculated as the end date of a regimen minus the start date of the corresponding regimen and will be computed during the analytics phase of the project (Table 5).
- Time under observation for analysis of rwEFS/rwRFS, by line, based on start date of treatment within line and dates of R/R event or disease progression, or censoring (Table 5-Table 7).
- Time under observation for analysis of rwOS from start of the first qualifying Mylotarg-containing R/R-based line of therapy, based on start of treatment in the first qualifying line setting, and based on date of death or censoring (Table 8).

- Time to best response for each regimen in the first qualifying Mylotarg-containing R/R-based line of therapy from the index date through the end of the third R/R-based line of therapy or the end of the record, whichever occurs first (Table 9-Table 11, Table 14-Table 15).

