Demographic and clinical characteristics will not be stratified by a primary grouping variable.

#### 4.3.4. Methods under Objective 2

*Objective 2: To describe the treatment patterns from the diagnosis of AML through the end of the third R/R-based line of therapy.*

Analysis under this objective will include all study patients. Descriptive analysis as detailed in [Section 4.3.1](#) will be conducted for work under this objective. Treatment patterns include description of regimens within line of therapy for the first 3 R/R-based lines of systemic therapy as well as the description of sequences of regimens across the first 3 R/R-based lines of systemic therapy. Description of treatment regimens within line includes the frequency and percentage of each agent/regimen received, by regimen in sequence, by line, for the first 3 R/R-based lines of systemic therapy. In addition, the analysis will descriptively characterize the starting dose and dose changes of Mylotarg in each of the first lines of therapy.

Duration of treatment will also be descriptively analyzed across lines of therapy, starting with the first agent or regimen in the first line of therapy for the first 3 R/R-based lines of therapy.

### 4.3.5. Methods under Objective 3

*Objective 3: To describe the effectiveness outcomes of treatment of AML patients who received Mylotarg in a real-world setting*

Analysis under this objective will include all study patients. The outcomes of interest under this objective are rwEFS/rwRFS and rwOS. Time to event analysis as described in [Section 4.3.2](#) will be utilized.

The Kaplan-Meier product limit estimator will be employed to evaluate rwEFS/rwRFS and rwOS. The time origin for these analyses will be the start of the treatment in the respective line of therapy for rwEFS/rwRFS for the first 3 R/R-based lines of therapy. The time origin of rwOS analysis is the start of the earliest line of Mylotarg therapy. rwEFS/rwRFS and rwOS analyses for lines of therapy will be limited to patients who received treatment during the line of interest.

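### Table 4 reports Mylotarg dose for first-line therapy only, and the SAP's dose-change variable also stops at line 1, although Objective 2c asks for dose in each of three lines

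*SAP*

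**What the plan says.** **Objective.** SAP section 2, Objective 2c, asks for "Starting dose and dose changes of Mylotarg in each of the first 3 R/R-based lines of therapy". Protocol section 8 has the same item: "Starting dose and dose changes of Mylotarg in each of the 3/R/R-based lines of therapy".

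**Method.** SAP 4.3.4 (methods under Objective 2) says that "the analysis will descriptively characterize the starting dose and dose changes of Mylotarg in each of the first lines of therapy". It gives no number of lines and names no table. The matching sentence in Protocol 9.7.4 mentions starting dose only.

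**Eligibility.** SAP 3.4.1 requires "Receipt of Mylotarg at any point during first 3 R/R-based lines of therapy following initial AML diagnosis date", so first use in line 2 or line 3 qualifies.

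**Derived variables.** SAP 3.5.2 derives "Start and end dates and start and end dose of infused anti-cancer treatments from the index date through the end of the third R/R-based line". The next item in that list, dose changes, is cited to Table 4 and closes at the end of the first R/R-based line. Protocol 9.3.4 defines the same dose-change variable through the end of the third.

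**Shells.** Table 4 (SAP 7.2.2) has one line block, "First Line Therapy". It holds one set of "Starting Dose" statistics and four dose-change rows. Table 5, for Mylotarg duration, has separate first-, second- and third-line blocks.

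**The concern.** The shells tell the programmer what to produce. Here the only dose shell covers one line, and the variable behind its dose-change rows is cut off at the same point. A programmer who follows both will deliver a first-line dose table and have no prompt to go further.

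Two kinds of Mylotarg exposure would then go undescribed: the dose of patients who first receive it in line 2 or 3, and a later course in patients who also had it in line 1. The study sets out to describe real-world Mylotarg use in newly diagnosed and relapsed or refractory disease. A reader of the report could take a first-line dose summary as the dose summary for the whole cohort.

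**Working it through.** No power, alpha or event figure bears on this point, and the plan gives no number to reproduce. The check is a count of which lines have a planned dose output.

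**1. Lines required.** Objective 2c names three lines, for two items each (starting dose and dose changes).

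**2. Lines supplied, across all 15 shells.**

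| Shells | Content | Mylotarg dose rows |
|---|---|---|
| Tables 1 and 2 | Patient and disease characteristics | None |
| Table 3 | Agents and regimen sequence | None |
| Table 4 | Starting dose and dose changes | Line 1 only |
| Table 5 | Mylotarg duration, lines 1, 2 and 3 | None |
| Tables 6 to 8, and 13 | rwEFS, rwRFS, rwOS | None |
| Tables 9 to 12, 14 and 15 | Response | None |

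Dose coverage is 1 of 3 lines. Duration coverage, from Table 5, is 3 of 3.

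**3. Are the data there?** Starting dose: yes, since start and end dose of infused treatments are derived through line 3 in SAP 3.5.2. Dose changes: they are abstracted through line 3 (SAP 3.5.1.1), but the derived variable closes at line 1. The later-line dose-change rows therefore could not be filled until that window is changed.

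**4. Could the block label mean the first Mylotarg-containing line?** Hardly. The SAP writes out the longer expression in the titles of Tables 6 to 12 when it means that. Table 5, which comes next, uses the short label for line 1, followed by second- and third-line labels.

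**5. How many patients?** Let *p* be the share of patients who receive Mylotarg in line 2 or 3. The number with an unreported line-specific dose is *p* × N, with N between 20 and 30 (SAP 3.3). The documents give no value for *p*. At *p* = 0 the number is 0; at *p* = 1 it is 20 to 30. Nothing in the plan narrows that range.

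**6. After the change.** With second- and third-line blocks added, coverage is 3 of 3.

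**The case against.** **The SAP text still commits to the analysis.** A reader might infer that Objective 2c is abandoned, or that relapsed and refractory users drop out of the dose result by design. The documents do not support that. Objective 2c and SAP 4.3.4 both stand, and an incomplete shell does not cancel them. Shells in this SAP can also be abbreviated: most sample rows of Table 3 show line 1, although its footnote covers three lines. This objection stands, and it limits the point to a mismatch between text and output.

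**Rows may have been lost in reading the PDF.** An asterisk in Table 4 has no footnote beneath it, and Table 5 carries an asterisked footnote with no matching mark. The heading of SAP 7.2.2 also promises an overall summary and one by type of first-line therapy, and the shell shows neither. Some doubt remains. Lost rows are still an unlikely explanation. SAP 3.5.2 independently stops the variable cited to Table 4 at line 1, and Tables 1 and 2 repeat their headings where they continue, which Table 4 does not.

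**The SAP is allowed to modify the Protocol.** Protocol 9.7 says so, so the shorter window could be deliberate. But the SAP's own Objective 2c keeps all three lines, so the SAP would then disagree with itself.

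**The single N at the head of Table 4.** A reader might infer that first-line percentages will be diluted by patients without first-line Mylotarg. The SAP states no denominator for the four dose-change rows, the header is a placeholder, and the starting-dose statistics have their own n. The denominator is unspecified, which is worth settling, but no planned error is shown.

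**Weight.** Dose is a sub-item of a descriptive objective. SAP 4.1 names rwEFS/rwRFS, rwOS and response as the primary endpoints, and none of them is touched. That is fair.

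**Conclusion.** The point holds as an inconsistency between an objective and its planned outputs. Table 4 and the SAP 3.5.2 dose-change window stop at line 1, whereas Objective 2c in both documents and Protocol 9.3.4 run through line 3, and SAP 4.3.4 promises dose by line. Followed as written, 1 of the 3 required lines is covered, and any patient given Mylotarg in line 2 or 3 has no dose reported for that line.

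The number of patients is unknown, from none to all of the 20 to 30 expected; any narrower figure would rest on an assumed split by line. The conclusion assumes that the shell is complete as it reads, which the matching derived-variable window makes likely but does not prove. It concerns reporting only and implies nothing about which dose is right.

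**What to change.** - Give Table 4 first-, second- and third-line blocks in the layout of Table 5.
- In each block, set the n and the percentage denominator to patients who received Mylotarg in that line, and say so in a footnote.
- Add one row for starting dose at first Mylotarg use, in all patients.
- Label the dose rows as Mylotarg.
- Reconcile the dose-change window in SAP 3.5.2 with the third-line window in Protocol 9.3.4, so that the new dose-change rows can be filled.

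The cost is a shell edit plus a one-phrase change to a derived variable, using data already abstracted through line 3. The later-line blocks will be small, and individual values may have to be listed in place of summary statistics.

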**Table 5. Mylotarg Treatment Duration, by Line of Therapy**

Mylotarg Treatment Duration		N=xxx
First Line Therapy		
n		xx
Mean		x.x
SD		x.x
1 st Quartile		x.x
Median		x.x
3 rd Quartile		x.x
IQR		x.x
Min, Max		x.x,x.x
N=xxx		
Second Line Therapy		
n		xx
Mean		x.x
SD		x.x
1 st Quartile		x.x
Median		x.x
3 rd Quartile		x.x
IQR		x.x
Min, Max		x.x,x.x
N=xxx		
Third Line Therapy		
n		xx
Mean		x.x
SD		x.x
1 st Quartile		x.x
Median		x.x
3 rd Quartile		x.x
IQR		x.x
Min, Max		x.x,x.x

\* The time origin was the initiation of Mylotarg. The end point was the last date of gemtuzumab therapy, regardless of line of therapy (duration could continue into subsequent lines of therapy), study end date, or death, whichever came first.

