### 4.2. Regimens and Lines

For purposes of this study, a **regimen** will be defined as 1 or more anti-cancer agents given in combination, over a period of time, in which the following conditions hold:

1. All agents start within 30 days of the start of the first agent in the combination, unless the start of an agent later than 30 days after the start of the first agent is specifically indicated as planned at the time of the start of the first agent.
2. No agent is discontinued and replaced by another agent within 30 days of the start of the first agent in the combination.
  - a. All agents in the regimen must be discontinued for the regimen to be considered as discontinued. If only a single agent within a regimen is discontinued after 30 days, the regimen is assumed to be ongoing so long as the other agents are not yet discontinued.
3. No agent is held and then resumed after an interval of more than 63 days. A standard chemotherapy cycle is assumed to be 21 days; 63 days allows for a delay of 3 cycles of chemotherapy without a change in regimen.

Please note: These conditions do not dictate how detailed information about oncology medications is captured, or how medication start and end dates are recorded, regardless of the days' supply of any given prescription. Rather, the conditions are only used to define lines of therapy, and information about medications and days' supply is recorded as documented in the medical record.

Accordingly, unless the record indicates a planned delay in the start of an agent, the addition of a new agent to an existing therapy more than 30 days after start of the regimen constitutes a change of regimen. Holding of an agent for a brief period is not interpreted as a change of regimen. However, discontinuation and resumption of an agent after an interval of more than

63 days is interpreted as signaling a new regimen. Discontinuation of all agents in a regimen signals the end of the regimen. Occurrence of an R/R event or a disease progression does signal the end of a regimen. Continuation after R/R event or progression of a treatment being given before the R/R event or progression will be interpreted as a new regimen—albeit identical to the previous one. This scenario, treatment through progression, occurs in some settings, and is identifiable in study data with the coding rules described here.

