#### 4.3.2. Time to Event Analysis

Single time to event analyses will be conducted as specified under the study objectives. CCI [REDACTED]

Real-world time to event outcomes in this study will include:

- rwEFS/rwRFS for the first 3 R/R-based lines of therapy. rwEFS will be defined as the time from the treatment initiation date (for the first agent in the first regimen in the first line of Mylotarg-containing therapy) to the date of treatment failure (TF), relapse from Complete Response (CR) or better, or death from any cause, whichever comes first. TF is defined as failure to achieve CR or better following up to 3 cycles of Mylotarg. rwRFS will be defined as the time from the treatment initiation date (for the first agent in the first regimen in the first line of therapy) to the date of a relapse event, or death from any cause, whichever comes first.
- rwOS, from the first line of therapy through the end of record or death, whichever occurs first, and
- Duration of therapy across lines of therapy from the first line of therapy through the third R/R-based line of therapy.

The time origin for analysis of rwEFS/rwRFS is the start of therapy within each specific line of therapy, and the terminal event is the earlier of an R/R event or death. The time origin for analysis of rwOS is the start of therapy within the first line of therapy, and the terminal event is death. Patients who are not indicated to be deceased at last known contact (patients who are alive, or lost to follow-up) will be censored. The time origin for analysis of duration of therapy is start of Mylotarg, and the terminal event is discontinuation of that therapy.

#### 4.3.3. Methods under Objective 1

*Objective 1: To describe the demographic and clinical characteristics as outlined in the variable list below for patients diagnosed with AML who received Mylotarg in a real-world setting.*

Descriptive analysis as detailed in [Section 4.3.1](#) will be conducted for work under this objective. Demographic characteristics that will be reported will include sex, patient age, race/ethnicity, height, weight, BMI, insurance status, and region of residence closest to the index date. Clinical characteristics that will be reported will include comorbidities and comorbidity index score, ECOG score, and disease characteristics, such as stage at index date, cytogenetic testing at index date, and whether the AML diagnosis was de novo versus secondary.

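### SAP Table 5 is laid out by line of therapy, but its footnote runs Mylotarg duration across lines, and nothing says which block a multi-line patient enters

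*SAP*

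**What the plan says.** Objective 2d in SAP Section 2 is "Duration of Mylotarg treatment in each of the first 3 R/R-based line of therapy". Protocol Section 8 sets the same target: "Duration of Mylotarg treatment in each of the first three R/R-based line of therapy". Table 5 is titled "Mylotarg Treatment Duration, by Line of Therapy" and has separate first-, second- and third-line blocks, each with n, mean, SD, quartiles, median and range.

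Four other places bear on what goes into those blocks:

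- **Table 5 footnote.** "The time origin was the initiation of Mylotarg", and the end point is the last gemtuzumab date "regardless of line of therapy (duration could continue into subsequent lines of therapy"), or else "study end date, or death, whichever came first".
- **SAP 3.5.2, Derived Variables.** This cites Table 5 and computes duration as the regimen's end date minus its start date.
- **SAP 4.2, Regimens and Lines.** "Occurrence of an R/R event or a disease progression does signal the end of a regimen". Treatment carried on past such an event is a new regimen, and a new regimen after such an event is a new line.
- **SAP 4.3.2 and 4.3.4.** The first states: "The time origin for analysis of duration of therapy is start of Mylotarg, and the terminal event is discontinuation of that therapy". The second has duration analysed descriptively and across lines.

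**The concern.** A duration that may cross a line boundary is not a duration in a line. Under the footnote, a patient who has Mylotarg in first line, stops, relapses and receives it again in second line gets a first-line duration covering the first course, the whole interval off drug and the second course. The reader of Table 5 would take that figure as time on treatment in first line.

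The SAP also does not say whether this patient appears in one block or two, so two programmers following it could produce different tables. With 20 to 30 patients split over three blocks, a few such patients can dominate the mean, SD and maximum.

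**Working it through.** The plan gives no duration figure to reproduce, so the check compares definitions and then does date arithmetic on assumed patients.

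**Step 1: definitions side by side.**

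| Source | Starts | Stops | Confined to a line? |
|---|---|---|---|
| Objective 2d; Table 5 title and blocks | within line | within line | yes |
| SAP 3.5.2 with 4.2 | regimen start | regimen end, no later than the R/R event or progression | yes, but measures the regimen, not Mylotarg alone |
| SAP 4.3.2 | start of Mylotarg | discontinuation of Mylotarg | not stated |
| Table 5 footnote | initiation of Mylotarg | last gemtuzumab date in any line | no |

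**Step 2: two patients (assumed dates, days from first Mylotarg).** X is treated through an R/R event: first line days 0-40, second line days 40-70. Y is re-exposed: first line days 0-10, second line days 200-210. The footnote can be applied in three ways: (A) one entry, in the line of initiation; (B) an entry in both blocks, each timed from first Mylotarg; (C) an entry in both blocks, each timed from the Mylotarg start in that line.

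| | Within line (L1 + L2) | A | B | C |
|---|---|---|---|---|
| X | 40 + 30 = 70 | 70, no L2 entry | 70 + 70 = 140 | 70 + 30 = 100 |
| Y | 10 + 10 = 20 | 210, no L2 entry | 210 + 210 = 420 | 210 + 10 = 220 |

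The first-line entry is overstated under all three: by 70 - 40 = 30 days for X and 210 - 10 = 200 days for Y. Of Y's 200 days, 200 - 10 = 190 are off drug. Under A the second course is absent from the second-line block; under B and C it is counted twice.

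**Step 3: effect on the first-line mean.** Assume all N patients are in the first-line block with true duration d, and k of them have footnote duration D. The mean is then d + k(D - d)/N.

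| k | X type, d = 40, D = 70: N = 20 / N = 30 | Y type, d = 10, D = 210: N = 20 / N = 30 |
|---|---|---|
| 0 | 40 / 40 | 10 / 10 |
| 1 | 41.5 / 41.0 | 20 / 16.7 |
| 3 | 44.5 / 43.0 | 40 / 30 |
| 6 | 49.0 / 46.0 | 70 / 50 |

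For example, k = 1, Y type, N = 20: 10 + 200/20 = 20 days. The median does not move in any row, because all the other durations are set equal and k is below N/2.

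**Step 4: mean against median when durations vary.** Assume within-line durations uniform on 1-60 days (mean 30.5), and a share q re-exposed after a gap uniform on 180-365 days (mean 272.5) for a second course uniform on 1-60 days. The added time averages 272.5 + 30.5 = 303 days.

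- Mean = 30.5 + 303q.
- Variance = 59²/12 + q(185²/12 + 59²/12) + q(1 - q)303² = 290 + 3142q + 91809q(1 - q).
- Every re-exposed duration is at least 1 + 180 + 1 = 182 days, so for these q the median lies among the others: 1 + 59 × 0.5/(1 - q).

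| q | Mean | SD | Median |
|---|---|---|---|
| 0 | 30.5 | 17 | 30.5 |
| 0.1 | 60.8 | 94 | 33.8 |
| 0.2 | 91.1 | 125 | 37.9 |
| 0.3 | 121.4 | 143 | 43.1 |

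The mean and SD are heavily exposed; the median moves by about 3 to 13 days.

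**The case against.** The strongest defence is that cross-line duration is deliberate and disclosed. Section 4.3.2 runs from start of Mylotarg to its discontinuation with no stop at a line boundary, Section 4.3.4 speaks of duration across lines, and the footnote tells the reader what was done. This stands in part: the footnote is not a stray error, and editing it alone would leave the methods text in conflict with the table. It does not rescue the by-line title or answer Objective 2d. Section 4.3.2 is not clear support either, since Section 4.2 lets a provider-documented stop for any reason count as discontinuation, which could end the clock in first line even if the drug is restarted.

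A second defence is that Section 4.2 ends regimens, whereas Table 5 measures one agent, and Section 4.2 says its conditions do not govern how medication dates are recorded. That is fair: the regimen rule does not by itself set a Mylotarg stop date. The firmer conflicts are with Objective 2d and with Section 3.5.2, which names Table 5.

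A reader might infer that the table will necessarily contain inflated and double-counted durations. The documents do not support that. The footnote says only that duration could continue, no frequency of multi-line use is given, and a single entry per patient (reading A) counts nothing twice.

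One might also argue that Table 5 must be a Kaplan-Meier analysis because Section 4.3.2 lists duration among time-to-event outcomes. Section 4.3.4 says duration is analysed descriptively, and Section 4.3.5 prescribes Kaplan-Meier only for rwEFS, rwRFS and rwOS, so this is a preference.

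**Conclusion.** The point holds as a conflict of definitions. Followed as written, the footnote does not deliver what Objective 2d and the Table 5 layout ask for. For any patient with Mylotarg in more than one line, the earlier-line entry is overstated, and the later course is either lost from its block or counted twice, depending on a rule the SAP does not state.

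The size cannot be fixed from the documents. It is zero without multi-line use, modest for treatment through an R/R event, and potentially large for the mean, SD and maximum when there is re-exposure after a gap; the median is much less affected. All illustrative figures rest on assumed dates, durations and re-exposure shares. The outcome is descriptive and is not among the primary endpoints in SAP Section 4.1, and no test, alpha or power is involved. It should be corrected, but it does not threaten the study's main results.

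**What to change.** Reconcile Objective 2d, SAP Sections 3.5.2, 4.3.2 and 4.3.4, and the Table 5 footnote on one definition:

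1. Within each Table 5 block, run duration from the first to the last Mylotarg date in that line, stopping at the R/R event or progression that ends the line if that comes first.
2. Enter a patient with Mylotarg in several lines in each of those blocks, with that line's exposure only, and state how gaps within a line are handled.
3. If total exposure is wanted, add a separate row labelled any line, one entry per patient, and say that it includes time off drug between courses.
4. In Section 3.5.2, separate regimen duration from Mylotarg duration, since under Section 4.2 a regimen continues until all its agents have stopped.

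A Kaplan-Meier median that censors patients still on Mylotarg at the last record is an optional addition.

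The cost is a few SAP sentences and minor programming. Treatment dates through the third line are already collected under SAP Sections 3.5.1.1 and 3.5.1.2. Protocol Section 9.7 allows the SAP to modify the protocol's plans and reserves amendments for major changes to primary endpoints, so a SAP revision should suffice.
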